8.2 STATISTICAL ANALYSES

- **Analysis of Primary (Efficacy) Endpoint**

The primary (efficacy) analysis will be conducted in the FAS analysis population. The proportion of Achievement rate for LDL-C at Week 12 defined as the primary endpoint will be analyzed by calculating a point estimate with confidence interval (CI).

Achievement rate for LDL-C will be summarized overall, within each CVD risk strata, and by dose group within each CVD risk strata. 95% confidence intervals will be estimated.

In addition, percentage of patients who achieve LDL-C therapy target will also be tabulated by sex, age group, dose group and baseline disease type.

- **Secondary Endpoints and Safety Analyses**

Analysis of lipid values and change and percent change in lipid values at week 12 will be performed on the FAS populations. Analysis of the remaining secondary endpoints and safety data will be done on SAS (See [Section 5.2](#)). Data summaries will be presented in tabular and/or and summarized descriptively, where appropriate.

Lipid Parameters

Descriptive summary will be tabulated overall and by dose group within each CVD risk level for percent (%) change from baseline for TC, HDL-C and LDL-C and TG at Week 12.

Study Drug Exposure

Exposure to atorvastatin will be summarized descriptively overall, and by CVD risk level. Duration (days) of study drug taken, daily dose, dose at week 12, and total dose will be summarized. Listings of dosing records with the reason of change dose will also be provided.

Adverse Events

Adverse events will be classified using the medical dictionary for regulatory activities (MedDRA) classification system. The severity of adverse events will be graded according to the principal investigatory judgment and collected in CRF.

Adverse events (such as treatment emergent adverse events; treatment-related adverse events; and serious adverse events, adverse event from early termination to final visit, will be summarized by system organ class (SOC) and preferred term (PT) according to MedDRA terminology.

Adverse events will be summarized overall and by dose group within each CVD risk strata by SOC and preferred term.

Adverse events of special interest ([section 6.2](#)) will be tabulated by preferred term (PT) overall and by dose group within each CVD risk level.

Adverse events leading to discontinuation of trial treatment will be presented overall and by dose group within each CDV risk level.

Dropouts

Percentage of patients who drop out of the study and reasons for discontinuation will be summarized overall and by dose group within each CVD risk level.

Laboratory Data

The percentage of patients with abnormal laboratory values will be summarized overall and by dose group within each CVD risk level for CK, Aspartate Aminotransferase (AST), and Alanine Aminotransferase (ALT).

Descriptive summary will be provided for change from baseline for clinical laboratory by overall and dose group within each CVD risk level.

The baseline is the last non-missing value prior to treatment start.

Prior and Concomitant Medications

Prior and concomitant medications will be coded by WHO medical dictionary; patients who received these medications will be listed and summarized overall, and by dose group within each CVD risk level.

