6	21 st September, 2017	Substantial amendment	
5. MILESOT NES
 
8.2.2 Inclusion Criteria
 
8.2.7 Study Procedures
	
1. Update the planned date of all the milestones per the latest progression
 
2. Allow to collect the baseline lab reports within 24h after starting atorvastatin therapy
 
3. Change the time limit of unplanned visits to “any date during Week 4 to Week 16 (D29 to D115(±10 days))”
	
Change the Milestones according to the actual execution
 
Make the study design closer to clinical practice

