### **8.2.2. Inclusion Criteria**

Patients must meet all of the following inclusion criteria to be eligible for inclusion in the study:

- Men and women aged  $\geq 18$  years;
- Cardiology patients# who has been prescribed atorvastatin by physician's clinical judgment under normal clinical care. These patients will include those with established coronary heart disease, or having multiple risk factors and at risk for cardiovascular disease, or primary hypercholesterolemia.
- Baseline laboratory reports\* prior to starting atorvastatin therapy can be tracked, including lipid measurement, liver function, creatine kinase (CK) value, and renal function.
- Evidence of a personally or his/her legally acceptable representative signed and dated informed consent document indicating that the patient has been informed of all pertinent aspects of the study and accept follow-up visit.

#The proportion of ward inpatients is not more than 20% of the total number of patients.

\*The date of the report should be within 1 month before taking atorvastatin or within 24h after starting atorvastatin therapy.

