### 8.2.7. Study Procedures

At baseline visit, patient inclusion/exclusion and demographic information, medical history, medication records, concomitant drugs and laboratory examination results prior to Atorvastatin therapy such as liver function, blood lipid parameter, creatine kinase value and renal function will be collected by investigators in the study. At week 12 visit and any unplanned visits, the laboratory examination results and medication records will be collected. Adverse events will be recorded at any time during the study period.

Schedule of Activities is as follows:

Protocol Activity	Visits	Visit 1	Visit 2	Any unplanned Visits
		Baseline Day(D)1	Week 12 D85 ( $\pm 10$ days)	Any date during Week 4 to Week 16 D29~D115( $\pm 10$ days)
Signed Informed Consent Form		▲		
Demographic information		▲		
Medical history		▲		
Laboratory examination		▲*	▲	▲
Inclusion/exclusion criteria		▲		

Visits	Visit 1	Visit 2	Any unplanned Visits
Adverse event records	Record at any time during the study period		
Medication records	▲	▲	▲

Notes: Each activity refers to section **8.3 Variables**

\* The date of the report should be within 1 month before taking atorvastatin or within 24h after starting atorvastatin therapy

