2.1 STUDY DESIGN

Overview

This is a multi-center, prospective, observational study, which will be completed by Beijing Anzhen Hospital, Capital Medical University and approximately 64 other clinical sites.

At baseline visit, patient inclusion/exclusion and demographic information, medical history, medication records, concomitant drugs and laboratory examination results prior to atorvastatin therapy such as liver function, blood lipid parameter, creatine kinase value and renal function will be collected by investigators in the study. At week 12 visit and any unplanned visits, the laboratory examination results and medication records will be collected. Adverse events will be recorded at any time during the study period. Schedule of Activities is as follows:

Table 1: Schedule of Activities

Visits	Visit 1	Visit 2	Any unplanned visits
Protocol Activity	Baseline Day 1	Week 12 Day 85 (± 28 days)	Any Date During Week 4 to Study Close
Signed Informed Consent Form	▲		
Demographic information	▲		
Medical history	▲		
Laboratory examination	▲*	▲	▲
Inclusion/exclusion criteria	▲		
Adverse event records	Record at any time during the study period		
Medication records	▲	▲	▲

* The date of the report should be within 1 month before taking atorvastatin.

Study population

Judged by investigators, patients in cardiology department who are eligible for inclusion and exclusion criteria can be included into this study. Estimated total sample size is 10,000 and will be conducted in approximately 65 hospitals in China.

Data source

This Non-Interventional (NI) study data will be recorded in the medical records by investigators, and then input to electronic Data Collection (EDC) system as the form of electronic Case Report Form (eCRF).

Treatment/dose group

The study drug (atorvastatin) is from the doctor's prescription and will be recorded on Day 1, Week 12, and within Week 4 to end of the study. The analysis by dose groups will be taken the dose level recorded at Week 12 (Visit 2) on the prescription level or the last dose in the unplanned visit if the Week 12 is not available.

The dose groups will be in four daily dose levels, 10 mg, 20 mg, 40 mg and > 40 mg.

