11 APPENDICES

11.1 APPENDIX 1: DATA DERIVATION DETAILS

A1.1 Definition of visit windows

- Baseline (Day 1) is defined after informed consent date signed within one month prior to receive a study drug.
- Study Day = date of assessment – date of first dose of study drug + 1
- Week 12 is defined as Study Day 85 ± 28 days from the Day 1 study drug taken.
- Duration of Study Drug = Date of last dose – date of first dose +1
- End of Study: The Day completion of the study or discontinuation from the study.

A1.2 Demographic and Baseline Variables

- Demographic information : age, gender, height , body weight and BMI
- Medical histories:current or previous medical history, family history of premature atherosclerotic cardiovascular disease (ASCVD) and history of smoking
- Baseline Variables: strata
 - CVD risk level: low, moderate, high, very high, per definition in section 5.4.
 - Liver function tests: ALT, AST, total bilirubin (TBil)
 - Renal function tests: Creatinine (Cr), Blood Urea Nitrogen (BUN), Uric Acid (UA)
 - Serum lipid parameters :LDL-C, HDL-C, TG, Total-C
 - Creatine kinase value (CK)
 - Disease type: established CHD (Coronary Heart Disease), multiple risk factors, and hypercholesterolemia

A1.3 Definition of Derived Variables

Age

- Age = integer of [(informed consent date – date of birth)/ 365.25]
- Age groups: 18 – 64 years old, ≥ 65 years old

Body Mass Index (BMI)

- $BMI = \text{Weight (kg)} / [\text{Height (m)}]^2$

CVD risk level (strata)

The CVD risk level is based on Chinese Guideline on Dyslipidemia Prevention and Treatment in Adult (2007), the cardiovascular disease (CVD) risk stratification. The 10 years CVD risk factors are calculated based on age, sex, total cholesterol, HDL-C, hypertension, smoking history, medical history, and family history.

The CVD risk level for dyslipidemia will be derived.

Reference Normal Laboratory Ranges

The normal laboratory ranges will be defined by local lab facilities.

A2.1 SAS code for exact method

```
proc freq data=Lipitor order=freq;  
  tables LDL-C Goal / binomial (exact) alpha=.05;  
  title 'Exact methods of 95% confidence interval (CI) for rate of LDL-C' ;  
run;
```

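### The SAP defines baseline as pre-dose only and omits the protocol's 24-hour post-dose allowance, so some eligible patients can drop out of the change-from-baseline summaries

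*SAP*

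**What the plan says.** **Protocol.** The footnote to the laboratory criterion in section 8.2.2 reads "The date of the report should be within 1 month before taking atorvastatin or within 24h after starting atorvastatin therapy". The abstract and the note under the schedule in section 8.2.7 say the same. The post-dose part is item 2 of amendment 6 (21 September 2017), classed as substantial: "Allow to collect the baseline lab reports within 24h after starting atorvastatin therapy". The body text of sections 8.2.2 and 8.2.7 still describes these results as obtained before atorvastatin is started; only the footnotes extend the period.

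**SAP.** Baseline timing appears in three places:
- Section 2.1, Table 1 footnote: "The date of the report should be within 1 month before taking atorvastatin", with no post-dose clause.
- Section 8.2, Laboratory Data: "The baseline is the last non-missing value prior to treatment start".
- Appendix A1.1: "Baseline (Day 1) is defined after informed consent date signed within one month prior to receive a study drug".

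A1.1 also defines study day from calendar dates alone, with the first-dose date as Day 1. Section 7 rules out imputation for all endpoints. Section 1 lists one change from the previous SAP version, the Week 12 window, and records no decision to reject post-dose baselines.

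**The concern.** The two documents use different definitions of the same measurement. The protocol enrols a patient on the strength of a report that the SAP, as worded, cannot use. If the SAP is programmed literally, such a patient contributes a Week 12 lipid value but no change or percent change. Change from baseline in lipids is a secondary endpoint in SAP section 6.2, so its denominator would shrink for a reason that nobody appears to have chosen. A less literal programmer would keep some of these patients, so the result would depend on an unwritten decision.

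**Working it through.** **1. Which patients are affected.** Study day is the assessment date minus the first-dose date plus 1.
- *Report within 1 month before first dose, with or without a later one.* Both documents are satisfied, and the patient keeps a baseline unless A1.1 is read as requiring the value to follow consent (see fix).
- *Only report on the next calendar day, within 24 hours.* Study day = 1 + 1 = 2. The protocol accepts it. All three SAP statements exclude it.
- *Only report on the first-dose date, after the dose.* Study day = 0 + 1 = 1. Section 8.2 excludes it because it is not before treatment start, yet Table 1 labels Day 1 as the baseline visit. Protocol section 8.3 lists no sampling time, so a date-based program might accept it. The handling is ambiguous.

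SAP section 8.1 lets an unscheduled result be used if it qualifies as baseline. That does not widen what qualifies.

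**2. Which results lose them.** With no imputation (section 7), the patient leaves the change and percent-change lipid summaries (sections 6.2 and 8.2) and the laboratory change summaries (section 8.2), and has a gap in the baseline laboratory characteristics (section 8.3).

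**3. The primary endpoint.** Goal attainment compares the Week 12 LDL-C with a target set by risk stratum, so baseline LDL-C is not needed. Patients classed by diagnosis (coronary heart disease or an equivalent, acute coronary syndrome, ischaemic cardiovascular disease with diabetes) need no baseline lipids for their stratum. Appendix A1.3 derives 10-year risk partly from total cholesterol and HDL-C. For patients classed that way, a missing baseline could leave the stratum, and so the target, undetermined.

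**4. Size.** The documents give no count, so this is an illustration on stated assumptions.
- The plan's own sizes reproduce: 1.96² × 0.60 × 0.40 / 0.011² = 7,620, against 7,600 stated, and 7,600 / (1 − 0.24) = 10,000.
- Protocol section 5 gives data collection from June 2016 to October 2018. Assume 1 June 2016 to 31 October 2018. The last first dose with Day 85 inside that period is 31 October minus 84 days = 8 August 2018.
- Enrolment span: 799 days. Days on or after 21 September 2017: 322. 322 / 799 = 40.3%.
- With even accrual, 0.403 × 10,000 = 4,030 patients enrolled under the allowance.
- Assume 1% to 10% of these have only a 0 to 24 hour report: 40 to 403 enrolled. Among planned completers, 0.403 × 7,600 × 0.01 = 31 to 0.403 × 7,600 × 0.10 = 306.
- If the share is applied to all completers regardless of enrolment date: 76 to 760.
- At 306 lost, 306 / 7,600 = 4.0%, and a descriptive interval widens by about 1/√0.96 = 1.02, or 2%.

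The 31 to 306 range counts the whole 0 to 24 hour period; if same-date samples are accepted, it is smaller. Time for ethics approval of the amendment (protocol section 9.3) lowers it further. Protocol section 8.2.6 still shows a last visit in December 2016, before the amendment. Section 5 is used because amendment 6 updated it.

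**5. A secondary difference, the Week 12 window.** Protocol: 85 ± 10 = Day 75 to 95, 21 days. SAP: 85 ± 28 = Day 57 to 113, 57 days. The comparability argument in SAP section 1 concerns 8 weeks, the early side; none is given for Day 96 to 113.

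**The case against.** The strongest reply is that an eligibility window and an analysis baseline need not coincide. A strictly pre-dose baseline is a defensible choice, and the SAP agrees with the protocol's body text. This stands in part. The protocol does contradict its own footnotes, and correcting the SAP alone would leave that in place. However, nothing in the SAP presents the exclusion as a choice.

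It can also be said that the section 8.2 sentence sits under Laboratory Data, while the lipid paragraph has no baseline rule. That is true, but protocol section 8.3 counts lipids as laboratory examination, and the other two SAP statements are pre-dose as well.

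Four stronger readings are tempting and are not supported:
- *Every patient with a post-dose sample loses the baseline.* Those who also have a pre-dose report do not lose it through this omission, and same-date samples are ambiguous.
- *Hundreds of patients are lost.* The 1% to 10% share has no basis in the documents.
- *The SAP was written against a superseded protocol.* Table 1 also has unplanned visits at "Any Date During Week 4 to Study Close" where the protocol schedule has "Any date during Week 4 to Week 16", another amendment 6 change. That is consistent with an older base text, but the SAP's date is not visible and it cannot be shown.
- *The Week 12 window was changed improperly.* The change is disclosed with a reason, and protocol section 8.7 permits SAP modifications, requiring an amendment only for major ones to the primary endpoint. Whether this one is major is a judgement.

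**Conclusion.** The mismatch is real in the current text of both documents. As worded, the SAP gives no baseline to an eligible patient whose only report is post-dose within 24 hours. The result is certain for next-day samples and unsettled for same-date ones. The effect falls mainly on descriptive secondary results, and the study tests no hypotheses (SAP section 4.1).

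A reader might infer that the primary goal rate is biased. The documents do not support that beyond the subset whose stratum depends on a calculated 10-year risk, and the size of that subset is not given. The patient counts rest on even accrual, the assumed calendar dates and an assumed share, so they show scale only. Severity is minor to moderate. The Week 12 difference is a separate, lesser matter of reconciliation.

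**What to change.** 1. Put one baseline rule in SAP section 8.2, the Table 1 footnote and Appendix A1.1, stated to cover lipids and all other laboratory values. Baseline is the last non-missing value within 1 month before first dose or, if there is none, the value within 24 hours after it, judged by date where times are not recorded. Apply it regardless of consent date. A1.1 can be read as requiring the value to follow consent, whereas protocol sections 8.2.6 and 10 foresee patients already exposed at consent.
2. Report how many patients use a post-dose value.
3. Align the body text of protocol sections 8.2.2 and 8.2.7 with their footnotes.
4. Optional: state the same Week 12 window in both documents and add a table of the primary rate under ±10 days beside ±28 days.

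The cost is one SAP revision, a small protocol wording change and, if item 4 is taken up, one extra table. No new data are needed. The rule should be settled before data lock.

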8.3 OTHER ANALYSES

Subject Disposition

The number of patients screened and the number and percentage of patients enrolled and in each population will be summarized and listed for the enrolled population.

The number and percentage of patients who complete the study as well as the number and percentage of patients who discontinued the study drug and study will be summarized and listed. The primary reason for early discontinuation will be summarized and listed for all enrolled patients (EP).

Demographics and Baseline Characteristics

Demographic data (including age, gender, height, body weight and BMI) will be summarized by dose group. Baseline characteristics obtained from laboratory reports, including lipid measurement, liver function, creatine kinase (CK) value. Renal function and CVD risk level will be summarized by study dose group, and overall.

Baseline disease will be summarized in each dose group for established CHD, having multiple risk factors, and primary hypercholesterolemia.

Medical history at screening will be collected in the case report form and will be listed in a data listing.

Subgroup Analysis

Additional subgroup by risk factors and other exploratory analyses may be conducted as appropriate.

9 LIST OF TABLES AND TABLE SHELLS

The table shells will be provided by analysis team.

11 APPENDICES

11.1 APPENDIX 1: DATA DERIVATION DETAILS

A1.1 Definition of visit windows

- Baseline (Day 1) is defined after informed consent date signed within one month prior to receive a study drug.
- Study Day = date of assessment – date of first dose of study drug + 1
- Week 12 is defined as Study Day 85 ± 28 days from the Day 1 study drug taken.
- Duration of Study Drug = Date of last dose – date of first dose +1
- End of Study: The Day completion of the study or discontinuation from the study.

A1.2 Demographic and Baseline Variables

- Demographic information : age, gender, height , body weight and BMI
- Medical histories:current or previous medical history, family history of premature atherosclerotic cardiovascular disease (ASCVD) and history of smoking
- Baseline Variables: strata
 - CVD risk level: low, moderate, high, very high, per definition in section 5.4.
 - Liver function tests: ALT, AST, total bilirubin (TBil)
 - Renal function tests: Creatinine (Cr), Blood Urea Nitrogen (BUN), Uric Acid (UA)
 - Serum lipid parameters :LDL-C, HDL-C, TG, Total-C
 - Creatine kinase value (CK)
 - Disease type: established CHD (Coronary Heart Disease), multiple risk factors, and hypercholesterolemia

A1.3 Definition of Derived Variables

Age

- Age = integer of [(informed consent date – date of birth)/ 365.25]
- Age groups: 18 – 64 years old, ≥ 65 years old

Body Mass Index (BMI)

- $BMI = \text{Weight (kg)} / [\text{Height (m)}]^2$

CVD risk level (strata)

The CVD risk level is based on Chinese Guideline on Dyslipidemia Prevention and Treatment in Adult (2007), the cardiovascular disease (CVD) risk stratification. The 10 years CVD risk factors are calculated based on age, sex, total cholesterol, HDL-C, hypertension, smoking history, medical history, and family history.

The CVD risk level for dyslipidemia will be derived.

Reference Normal Laboratory Ranges

The normal laboratory ranges will be defined by local lab facilities.

A2.1 SAS code for exact method

```
proc freq data=Lipitor order=freq;  
  tables LDL-C Goal / binomial (exact) alpha=.05;  
  title 'Exact methods of 95% confidence interval (CI) for rate of LDL-C' ;  
run;
```

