2.3 SAMPLE SIZE AND POWER CALCULATIONS

In the recently published DYSIS [1] study, the achievement rate of Low-Density Lipoprotein Cholesterol (LDL-C) value was about 60% among Chinese outpatients taking 3 months lipid-lowering therapy. In this NI study, we assumed the achievement rate of LDL-C of 60%, allowable error rate of 1.1 %, type I error of 0.05, we calculated a required sample size of 7600 patients. Considering 24% loss to follow-up in real-world setting, the sample size will be 10,000.

This sample size will also allow for stratification by sex, age (<65 years vs \geq 65 years), risk stratification (very high risk, high risk, moderate risk and low risk) and baseline disease type (with established CHD, having multiple risk factors, and primary hypercholesterolemia).

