5.4 SUBGROUPS

Primary and secondary endpoints described in Section 6 will be summarized descriptively in all analysis populations except EP in these subgroups.

- **Age at Baseline**
 - 18 – 64 years old
 - ≥ 65 years old
- **Dose Groups**

The dose groups will be in four Atorvastatin daily dose levels:

- 10 mg
- 20 mg
- 40 mg
- > 40 mg

- **Baseline Variables**

Subgroup analyses may be performed within the following categories.

- CVD risk level: low, moderate, high, very high, per definition in [Table 2](#).
- Disease type: established CHD (Coronary Heart Disease), multiple risk factors, and hypercholesterolemia

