6 ENDPOINTS AND COVARIATES

6.1 PRIMARY (EFFICACY) ENDPOINT

- *The primary efficacy endpoint is the proportion of patients who achieve the LDL-C goal value. Achievement rate of LDL-C goals at 12 weeks of therapy of atorvastatin are evaluated according to Chinese Guideline on Dyslipidemia Prevention and Treatment in Adult (2007 version).*

$$\text{Achievement Rate} = \frac{\text{No. subjects who achieve LDL-C target value}}{\text{No. subjects who complete 12-week follow up}}$$

The Chinese Guideline on Dyslipidemia Prevention and Treatment in Adult (2007), the Cardiovascular Disease (CVD) risk stratification and LDL-C therapy target value are defined in Table 2.

Table 2: CVD Risk Stratification and LDL-C Therapy Target Value

Risk stratification	Beginning of drug therapy	Therapy target value
Low-risk: 10 years CV risk <5%	LDL-C \geq 4.92 mmol/L (190mg/dl)	LDL-C < 4.14 mmol/L (160mg/dl)
Medium/ Moderate risk: 10 years CVD risk 5% - 10%	LDL-C \geq 4.14 mmol/L (160mg/dl)	LDL-C < 3.37 mmol/L (130mg/dl)
High risk: CHD or CHD risk equivalents, or 10 years CV risk 10% - 15%	LDL-C \geq 2.59 mmol/L (100mg/dl)	LDL-C < 2.59 mmol/L (100mg/dl)
Very high risk: acute coronary syndromes, or ischemic cardiovascular disease combined with diabetes	LDL-C \geq 2.07 mmol/L (80mg/dl)	LDL-C < 2.07 mmol/L (80mg/dl)

Target achievement rate will be summarized overall, within each risk strata, and by dose within each risk strata. 95% confidence intervals will be provided.

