8 STATISTICAL METHODOLOGY AND STATISTICAL ANALYSES

8.1 STATISTICAL METHODS

SAS[®] Version 9.4 or later will be used to produce all listings and summary tables.

Summary tables presented by visit will include results from scheduled visits such as Day 1 and Week 12. Unscheduled visits will be listed but not summarized except in the event that an unscheduled result qualifies as a baseline result or other derived endpoint.

- **Analyses for Continuous Data**

Summary statistics for continuous variables/endpoints will be presented with number of observations (n), mean, SD, median, minimum (min), and maximum (max).

- **Analyses for Categorical Data**

Summary statistics for categorical variables/endpoints will be presented with number of observations (n) and percentages.

- **Analyses for Binary endpoints**

Exact methods (Clopper-Pearson Interval) will be used to calculate confidence interval (CI) for the primary (efficacy) endpoint: achievement rate of LDL-C at Week 12.

$$\left[\frac{r}{r + (n - r + 1)F_{1-\alpha/2;2(n-r+1),2r}}, \frac{(r + 1)F_{1-\alpha/2;2(r+1),2(n-r)}}{(n - r) + (r + 1)F_{1-\alpha/2;2(r+1),2(n-r)}} \right]$$

Where r is the proportion of patients who met therapy target level and n is the total number of patients who completed 12-weeks.

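### The SAP's template code for the exact interval does not fix goal achievement as the event, so any stratum or dose cell with under half at goal would show the non-achievement rate

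*SAP*

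**What the plan says.** SAP 6.1 fixes the endpoint: "The primary efficacy endpoint is the proportion of patients who achieve the LDL-C goal value". SAP 8.2 says where it is to be presented: "Achievement rate for LDL-C will be summarized overall, within each CVD risk strata, and by dose group within each CVD risk strata", with 95% intervals. The SAP uses four risk levels, and section 5.4 adds: "The dose groups will be in four Atorvastatin daily dose levels". That makes one overall estimate, 4 stratum estimates and up to 4 × 4 = 16 dose-by-stratum estimates.

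SAP 8.1 chooses the Clopper-Pearson interval and prints its F-quantile form, with the explanation: "Where r is the proportion of patients who met therapy target level and n is the total number of patients" completing 12 weeks.

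Appendix A2.1 supplies the code. The procedure line is "proc freq data=Lipitor order=freq", the request is "tables LDL-C Goal / binomial (exact) alpha=.05", and the title is "Exact methods of 95% confidence interval (CI) for rate of LDL-C". There is no `LEVEL=` option, no `BY` statement and no stratum variable. No other code for the interval appears in the SAP, and section 9 leaves the table shells to the analysis team.

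**The concern.** The `BINOMIAL` option of PROC FREQ analyses the first displayed level unless `LEVEL=` says otherwise, and `ORDER=FREQ` puts the most frequent level first. Together they estimate the proportion in the commoner category. That equals the achievement rate when at least half the patients are at goal, and its complement when fewer than half are. Which quantity is reported should follow from the endpoint definition, not from the data.

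If the template is carried into the stratified tables, only the low-achieving cells change, and each would look high-achieving under a title that refers simply to the LDL-C rate. Comparisons across risk strata and doses could then be reversed. The LDL-C targets tighten from below 4.14 mmol/L (low risk) to below 2.07 mmol/L (very high risk), so an overall assumption of 60% gives no assurance that every cell exceeds half. In a study with no hypothesis tests, these estimates and intervals are the main output.

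**Working it through.** **Inputs from the documents.** Assumed overall rate 60%, allowable error 1.1%, type I error 0.05, 7600 evaluable patients and 10,000 after 24% loss (SAP 2.3); Clopper-Pearson interval and its formula (SAP 8.1); required cells (SAP 5.4, 6.1, 8.2); code options (Appendix A2.1).

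**Assumed inputs.** Cell rates and cell sizes, because the documents give none. SAS was not available, so the template was emulated as the exact interval for the more frequent level.

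**1. The plan's own figures.** n = 1.96² × 0.6 × 0.4 / 0.011² ≈ 7619, against 7600 stated; the half-width at 7600 is 1.101%. 7600 / (1 − 0.24) = 10,000. Both reproduce.

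**2. The overall interval.** With r = 0.6 × 7600 = 4560 and n = 7600, the F-form in SAP 8.1 gives 58.9% to 61.1%, identical to the beta-quantile Clopper-Pearson limits. Achievers are the commoner level, so the template returns the same result. At a true 60%, the chance of an overall rate below half is about 10⁻⁶⁹.

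**3. A cell below half.** Let p be the percentage at goal, p < 50. The template reports 100 − p, so the error is (100 − p) − p = 100 − 2p percentage points, with mirrored limits. At exactly 50% the two levels give the same result. With an assumed n = 1000:

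| At goal | Correct rate (95% CI) | Template rate (95% CI) | Error, points |
|---|---|---|---|
| 300 | 30.0% (27.2 to 32.9) | 70.0% (67.1 to 72.8) | 40 |
| 400 | 40.0% (36.9 to 43.1) | 60.0% (56.9 to 63.1) | 20 |
| 450 | 45.0% (41.9 to 48.1) | 55.0% (51.9 to 58.1) | 10 |

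At 49% the error is 2 points (51% shown).

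**4. Small cells.** A true rate below 50% is not needed. With a true rate of 60%, the binomial probability that fewer than n/2 are at goal is:

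| Assumed cell size | Probability |
|---|---|
| 20 | 12.8% |
| 30 | 9.7% |
| 50 | 5.7% |
| 100 | 1.7% |

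**5. The definition of r.** The formula in SAP 8.1 is right when r is a count (step 2). Read literally, with r = 0.6 and n = 7600, it returns about 0.00% to 0.06%. PROC FREQ works from counts, so SAS output would not inherit this error.

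**The case against.** The strongest reply is that the fragment is illustrative. As printed it addresses one overall rate, for which it is correct at the planned 60%. The SAP does not say that it will be run by stratum. It cannot run unedited, because `LDL-C Goal` is not a standard variable name, so a programmer must rewrite it anyway. The SAP text makes clear that achievement is the event, SAS output labels the level analysed, and the planned counts and percentages would expose a reversal. The correct figure is the complement of the one shown, and no decision rule depends on it. Chance reversals in small cells would also tend to be modest: 9 of 20 at goal would appear as 55% instead of 45%.

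Most of this stands and limits the point. The harm is conditional on reuse, is detectable and leaves the overall result untouched. It does not clear the code, though. That the text fixes achievement as the event is exactly why code that follows the commoner outcome is inconsistent with it. The SAP requires intervals in the cells and offers no other code, and someone who corrected only the variable name and added a `BY` statement would keep the fault. A pre-specified template should not depend on a later check to catch it.

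**Conclusion.** The point holds. The code in Appendix A2.1 does not estimate the endpoint defined in SAP 6.1; it coincides with it only where at least half the patients are at goal. The overall primary result is safe at the assumed 60%. In any stratum or dose-by-stratum cell below half, reuse of the template would misstate the rate by 100 − 2p points: 20 points at 40% and 40 points at 30%.

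Three things are assumed: the standard behaviour of PROC FREQ, reuse of the template for the cells, and the illustrative cell rates and sizes. Which cells would be affected, if any, cannot be told from the documents. The wording of r in SAP 8.1 is a separate definition error with no effect on SAS output. Both should be corrected before programming; neither affects the design or the choice of method.

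**What to change.** In Appendix A2.1, remove `ORDER=FREQ`, use a valid variable name and name the event level, for example `TABLES GOAL / BINOMIAL(EXACT LEVEL='Yes') ALPHA=.05;`. State that the same code is run overall, by risk stratum, and by dose group within risk stratum. Word the title so that it says achievement of the LDL-C goal.

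In SAP 8.1, define r as the number of patients who met the target.

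The cost is a few lines of template code and one phrase of text, with no change to data, design or analysis method.
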